12.3 Reporting of side effects

As we are testing a relatively new procedure, all AEs will be reported at every follow-up.

All AEs will be assessed by the investigators and sponsor for association with the study drug and possible causality and reported according to present law. The severity of the AE and the possible association to the study drug will be evaluated according to following guidelines by investigators and sponsor:

1. **Not related** – No temporal association, other reasons/etiologies most likely cause of AE
2. **Possibly related** – Lesser clear association, other reasons/etiologies could be cause of AE.

3. **Likely related** – Clear temporal association with improvement in discontinuation of study drug, and not reasonably explained by the clinical condition of the patient.
4. **Related** – Clear temporal association with treatment or clinical assessment.

Patients experiencing AEs will be monitored with relevant clinical assessments and laboratory tests at the discretion of the attending and treating physician. All AEs will be followed until satisfactory restitution or stabilizing of the patient. Time of origin and ending, level of severity and consequences for the patient and study will be reported.

A Serious Adverse Event (SAE) is not dose-dependent and results in a significant risk of death or disability for the participant, including, but not limiting itself, to an event that:

1. causes death.
2. is life-threatening - the participant was at imminent risk of dying from the adverse event, according to the investigator's assessment.
3. requires hospitalization or prolongs already occurring hospitalization.
4. causes permanent disability.

All SAEs must be reported by investigators to sponsor within 24 hours from time of discovery.

Investigators are responsible for the registration, monitoring and reporting of all AEs and SAEs in the patient CRF and in the specific Trial Master File. Sponsor is responsible for the ongoing surveillance of the risk/benefit ratio in the study. If situations with risk or danger for the patient's safety or the execution of the study should occur, this must always and immediately be reported to the Danish Medicines Agency. Reporting of such situations or risks must also be done to all involved investigators and the approving ethics committee.

A safety report including all SAE and SAR must be made once a year and reported to the Danish Medicines Agency and the approving Ethics committee.

In case of a SUSAR, the sponsor must report this to the Danish Medicines Agency, the Ethics Committee and all investigators within 7 days, and within 8 days after the first reporting of the SUSAR, the sponsor must inform and share any relevant information from the sponsor and the investigators follow-up actions to the SUSAR with the Danish Medicines Agency.

Upon finishing the study an elaborate report containing all occurred SAEs must be made and reported to the Danish Medicines Agency and the approving Ethics committee. The sponsor will notify the Danish Medicines Agency no later than 90 days after completion of the trial, and if earlier than planned, reasons for stopping the trial.

13. Information and consent

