1.1 Background

Total knee arthroplasty (TKA) is a frequently performed procedure and is expected to increase in numbers due to the aging population and growing obesity rates [1-6]. Fast-track regimes with multimodal opioid-sparing analgesia have improved postoperative outcomes [7, 8]. However, a subset of patients still experiences unsatisfactory levels of postoperative pain in the weeks following surgery [9-12], potentially delaying mobilization and recovery as well as increasing the need for opioid analgesics. Current recommendations for pain management following TKA according to the Procedure Specific Postoperative Pain Management (PROSPECT) Working Group include paracetamol, nonsteroidal anti-inflammatory drugs (NSAIDs), glucocorticoids, local infiltration analgesia, and single shot adductor canal block (ACB) [12]. However, the role of ACBs for pain after TKA has been under extensive debate in recent years. While an ACB may provide some pain relief, the duration of pain control is usually less than 24 h and the effect on length of stay (LOS) and opioid consumption is questionable [12].

In the past decades, cryoneurolysis has been used to treat acute pain following herniorrhaphy [13], tonsillectomy [14], and thoracotomy [15] via the surgical incision. The emergence of percutaneous cryoprobes and the use of ultra-sound guided techniques has allowed for an increase in potential applications [16]. Recently, the use of cryoneurolysis has gained attention as a potential regional anesthetic technique for the treatment of knee pain. Cryoneurolysis works by freezing peripheral nerves with temperatures in the range of -20°C to -100°C, causing a Wallerian degeneration of nerve axons distal to the treatment site [17]. This process involves loss of the relative continuity of the axon and its covering of myelin but with a preservation of the surrounding endo-, peri-, and epineurium, thus allowing normal axonal regeneration and remyelination. Axons regenerate at a rate of 1-2 mm/day. Thus, resulting in a nerve block that typically will resolve with full recovery within weeks to months depending on the site of treatment [17].

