8.2 Intervention

The intervention will take place after the inclusion at 20-32 h after TKA surgery. The procedure will be performed at the Dept. of Anesthesiology.

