9.1 Ropivacaine

The cryoneurolysis intervention itself does not involve any study drugs. However, ropivacaine 5 mg/ml will be administered preceding the cryoneurolysis or the sham block. The ropivacaine is contained in plastic ampules.

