11.2 Study-specific considerations and risks

The study assumes that a further reduction in postoperative pain and rescue-opioid consumption after TKA is possible with postoperative cryoneurolysis compared to a sham block. This could secure a better postoperative convalescence and rehabilitation as well as lower the risk of complications.

Cryoneurolysis has been used to treat acute pain following herniorrhaphy [13], tonsillectomy [14], and thoracotomy [15] via the surgical incision. Recently, cryoneurolysis has been used for the treatment of knee pain. In May 2019, the United States Department of Health and Human Services published a report recommending the use of cryoanalgesia as a treatment option for knee pain due to osteoarthritis [33]. At Hvidovre Hospital cryoneurolysis is offered to selected patients with chronic post-herniorrhaphy pain. However, it is not part of standard care for acute post-TKA pain but the anesthetist performing the procedure is well trained.

Patients will receive cryoneurolysis of the ISN and ACFN nerves or a sham block at the same locations. The procedure will be performed with conscious patients after the injection of local anesthesia. The patient may experience tingling and slight pain in the area, but the procedure may be stopped at any time should the patient wish to. The control group will receive a sham-block using only local anesthesia and the insertion guide of the cryoprobe without freezing. The cryoprobe will be held close by for blinding purpose.

Generally, side effects following cryoneurolysis are mild and self-limiting [18]. Some patients experience mild to moderate pain involved in the initial application (first freeze sequence), but this usually resolves within 30 s. The most commonly reported side effects are bruising, numbness, redness, tenderness upon palpation, and swelling [20]. Due to the risk of

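### The causality scale in 12.3 asks for improvement on stopping a drug, which a one-time procedure cannot show afterwards, and sets a lower bar for Related than for Likely related

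*Combined protocol and SAP*

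**What the plan says.** Section 12.3 introduces the scale thus: "The severity of the AE and the possible association to the study drug will be evaluated according to following guidelines by investigators and sponsor". The upper three grades read:

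- Grade 2, Possibly related: "Lesser clear association, other reasons/etiologies could be cause of AE"
- Grade 3, Likely related: "Clear temporal association with improvement in discontinuation of study drug, and not reasonably explained by the clinical condition of the patient"
- Grade 4, Related: "Clear temporal association with treatment or clinical assessment"

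Grade 1 (Not related) covers events with no link in time and another most likely cause.

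On the treatment itself, section 8.2 states: "The intervention will take place after the inclusion at 20-32 h after TKA surgery". Section 8.2.2 describes one session, with ropivacaine around the nerves followed by cryoneurolysis or sham. Section 9.1 adds: "The cryoneurolysis intervention itself does not involve any study drugs". Section 1.1 describes the lesion as "resulting in a nerve block that typically will resolve with full recovery within weeks to months". Section 11.2 lists the usual effects: "The most commonly reported side effects are bruising, numbness, redness, tenderness upon palpation, and swelling".

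Section 12.2 defines an adverse reaction by its relation to the intervention drug and builds SAR and SUSAR on that definition. Neither 12.2 nor 12.3 says which of the four grades make an event an adverse reaction.

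**The concern.** The scale is written for a drug that is given repeatedly and can be withdrawn. This trial gives one procedure whose effect is meant to outlast it by weeks or months. A grade that depends on withdrawal therefore has almost no use here, and the grade above it drops the requirement to consider other causes.

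At stake is the label on each event. Relatedness determines whether an event is an adverse reaction, whether a serious event is a SAR, and whether a SUSAR with its 7-day notification arises. The protocol itself calls the procedure relatively new and follows patients for 6 months because its effects may last, so these labels will be read closely.

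**Working it through.** No arithmetic applies, and the plan gives no figure to reproduce. The check sets the four criteria side by side and runs typical events through them.

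| Grade | Timing | Improvement on stopping | Other causes |
|---|---|---|---|
| 1 Not related | no link | not asked | another cause most likely |
| 2 Possibly | less clear | not asked | another cause could explain it |
| 3 Likely | clear | required | clinical condition must not reasonably explain it |
| 4 Related | clear, or clinical assessment | not asked | not asked |

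**Step 1: can grade 3 be met?** Sections 8.2 and 8.2.2 describe one session and no repeat treatment. Section 11.2 lets the patient stop the procedure while it is under way, so pain during freezing could improve on stopping. Once the session is over, nothing remains to discontinue. An event that fades as the nerve recovers improves with time, not with withdrawal. Grade 3 is therefore open to events during the session and closed to those arising after it.

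**Step 2: are grades 3 and 4 ordered?** The grade 4 wording has two natural readings. Either clear timing relative to treatment suffices, with clinical assessment as an alternative route, or the timing may be relative to either treatment or assessment. Neither reading adds improvement on stopping or exclusion of other causes. Grade 3 asks for clear timing plus two further conditions, so every event that meets grade 3 also meets grade 4. The top grade is the easier one.

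**Step 3: run events through the scale.**

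- *Pain during freezing that eases on stopping, with no other explanation:* meets grades 3 and 4 together. The text gives no way to choose.
- *Dysesthesia at 2-14 days, clear timing, no other explanation:* fails grade 3 for want of discontinuation. It does not fit grade 2, where timing is less clear and another cause is available. It meets grade 4.
- *Bruising, swelling or tenderness soon after the session:* meets grade 4 on timing. If surgery is the likely cause, it also matches the other-cause half of grade 1 or 2, but not the timing half. The scale gives two answers.

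**Step 4: can timing discriminate?** The session takes place 20-32 h after knee replacement in every patient, and both arms receive the injection. Bruising, swelling and tenderness are listed effects of cryoneurolysis. That they are also ordinary early effects of knee replacement is a clinical assumption, not a statement in the documents. If it holds, these events follow both procedures closely in both arms. Under section 6.2 the assessing investigators and the sponsor are blinded, so the written criteria must carry the judgement.

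**The case against.** The strongest reply is that little depends on the grade, and much of it stands. Section 12.3 has all adverse events reported at every follow-up, whatever their relatedness. Section 8.3 has dysesthesia and other side effects evaluated at each follow-up, and the NeuPPS questionnaire is repeated each time. All SAEs go to the sponsor within 24 hours and appear in the annual and final reports. No analysis in section 7.2 uses the grade. Because grading is blinded, noise in it should be similar in the two arms. Bruising and swelling would not ordinarily be serious, so they would rarely reach SAR or SUSAR.

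A reader might infer that the scale hides a true difference in harm between arms. The documents do not support that: events can be compared by arm without any grade, and no tabulation of related events is planned. Nor do they support the inference that grade 3 is out of reach for every event, or that clearly timed dysesthesia is pushed down to Possibly related. Pain during freezing can meet grade 3, and that dysesthesia falls in Related, the cautious direction.

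It is also fair that grades 1 and 2 give an assessor words for a surgical cause. They do so only together with absent or weaker timing, so they do not settle a clearly timed event that surgery may explain.

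What the reply leaves untouched is that the rule, as written, does not order the evidence and rests one grade on a condition that this intervention cannot supply afterwards.

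**Conclusion.** The point holds as a defect in a stated rule. For any event arising after the session, one of the four grades is unavailable, and the top grade can be reached on timing alone. Events can be misgraded; whether any will be is not known. The consequence is limited to relatedness labels and to the AR, SAR and SUSAR classes that use them, and it is made worse by the absence of a rule on which grades count as an adverse reaction. The primary outcome, the all-event safety comparison and SAE reporting to the sponsor are unaffected.

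It is tempting to size the problem from the dysesthesia rate cited in 11.2: 22 × 2/169 = 0.26 expected severe cases in the cryo arm. That figure reflects the small sample and does not measure the fault in the scale. No count of misgraded events can be derived from the documents.

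The conclusion rests on the plain reading of grade 4 and on there being one session per patient. The difficulty with bruising, swelling and tenderness also rests on the clinical assumption stated above.

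**What to change.** In section 12.3:

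1. Replace the study drug with the study intervention, meaning the ropivacaine injection plus cryoneurolysis or sham. Blinded assessors can then grade against the whole session.
2. In grade 3, replace the discontinuation condition with criteria suited to a one-time procedure: clear timing, location consistent with the treated area, and no reasonable explanation by the surgery or the patient's clinical condition.
3. Require grade 4 to meet all grade 3 criteria plus a recognised mechanism.
4. State which grades count as an adverse reaction for section 12.2.

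The criteria should use only information already collected by blinded assessors and at telephone follow-up. Sensory mapping of the treated nerve should not be among them: it cannot be done by telephone, section 4.3 allows no extra visits, and numbness found in the treated area could reveal allocation.

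The cost is a few lines in 12.3 and matching CRF options, with no added visits or staff.

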13.1 Recruitment

Patients planned for TKA are screened in accordance with the inclusion and exclusion criteria and informed at the pre-surgery examination or anesthetist appointment or via phone before the surgery. Patients receive written information about the study before the surgery date and is told to consider their possible participation. If the patient declines all contact to the research personnel, the investigator is informed. If not, the patient is contacted for further information.

Patients who are found fit to participate is given adequate oral information about the study purpose, setting, advantages and risks.

An electronic screening log is kept tracking declining patients and later to fulfill the Consort diagram. This log does not contain names or other person-specific information, which would allow for future identification. The screening log is kept for later examination of the study cohort, and reasons for declining participation. No study related data is part of the screening log.

13.2 Informed consent

The information will be given without disturbance and interruptions and the patient is informed that he/she can schedule a new information interview and to bring a bystander/relative if wished. The information interview will be postponed until the bystander is present if requested. The information interview can be by attendance at the facility or by phone.

The patient receives the written information for participants at the pre-surgery appointment or if needed by secure email. The patient is informed that he/she is entitled to at least one day of reflection/consideration. If the patient does not want to participate, they can do so without informing about the reason for this.

The investigator or research-nurse informs the patient and collect the signed consent form. When needed, in case of sickness or holiday, other research collaborators can collect the signed consent form. The signed consent will be done before the surgery. Both the hospital and the patient will have a signed Consent form. The applicable guidelines and restrictions concerning informed consent brought by the National Ethics Committee is attached to the patient-information. Information for the participant and the Consent form is attached as Appendices 2 and 3.

The patient will be informed that participation is voluntary, and that withdrawal can happen anytime without justification, also after the signed consent, without this affecting their further treatment course and stay at the facility. They will also be informed that the investigator can pull them out of the study anytime at their discretion.

14. Information from the electronic patient journal

All information from the EPJ will be obtained after signing the informed consent form the day after surgery. The consent gives the primary investigator, the sponsor, and sponsor's representatives direct access to gather information from the patient's journal including the EPJ. The information obtained is necessary for the completion of the study and to make sure that the study is carried out correctly, which includes self-control and quality control. After the informed consent, the following information will be obtained from the patient's EPJ:

- Gender
- Age
- Height
- Weight
- Co-morbidities
- American Society of Anesthesiologist (ASA) score

- Pain Catastrophizing Scale (PCS)
- Current medical prescriptions (including glucocorticoids, immunosuppressants, opioids, insulin, and anti-psychotics)
- Surgical data (date of surgery, indication, surgical time, procedure information, intraoperative bleeding, transfusion data, perioperative analgesics)
- Type and dose of rescue-analgesics (opioids) or other specific pain-relieving actions that differ from standard treatment during the in-hospital stay
- Adverse events throughout the hospitalization
- Morbidity and mortality during the in-hospital stay at each follow-up

15. Data protection

The study will be conducted according to the General Data Protection Regulation and The Data Protection Act. All information will be treated confidentially, and all data will be pseudonymized with a code.

All research personnel are subject to professional secrecy. The investigators will keep an ID-list on all patients included in the study, containing full name, social security number and participant-ID.

A screening log is kept electronically in REDCap containing date of screening/surgery, age, reasons for not including in study on all patients screened for participation.

Collected data will be entered in the electronic CRF. This CRF and the EPJ will be made available for third parties in accordance with Danish Law. This means available for inspection by the Danish Medical Agency or other health authorities.

Patients will be informed that results will be stored and analyzed, and that anonymity will be respected. Data will always be stored in accordance with the regulations by DPA.

Furthermore, participants will be informed of the possibility of inspection of the data from public authorities. Investigator ensures that the study follows the principles of Good Clinical Practice.

16. Quality monitoring and assessment

At Hvidovre Hospital, the quality related to the study and the treatment of study participants will follow the usual quality monitoring and assessment.

17. Practical information

17.1 Financial conditions

The initiative to the study has been taken by [name] [name] and [name]. Expenses are held by [name] and [name] who has received funding to the study from the Candys Foundation. The primary investigator [name] is employed as a ph.d.-student and is paid according to the collective agreement for medical doctors in Denmark. Study specific expenses include cryoneurolysis probes with a total cost of 77,000 DKK (22 probes priced at 3.500 DKK) as well as salary for [name] (1 year) and costs associated with presentation of results at scientific

conferences. The total amount expected to complete the study is approximately 700,000 DKK. The whole amount is provided by funds from the Candys Foundation.

None of the participating investigators, research personnel, or sponsors have any economical yield/gain from the study.

In case further funding is obtained to this study, the participants and Ethics Committee will be informed.

All funding is managed through an account which is subject to public audit.

17.2 Patient completion and interruption of the study

A patient who has completed the study, must have received the study drug, and the primary outcome registration must have been completed as described in this protocol.

A patient who interrupts the study, must have been included from the start, have given signed consent and have been given the study intervention, but not completed the primary outcome for any reason. If a subject interrupts the study the data collected will be used after acceptance from the patient. If the patient wishes that the collected data from acceptance to withdrawal from the study shall not be used, this data will be deleted. In case of interruption of the study, the patient will continue usual care following the standard fast-track treatment including pain medication.

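### Section 17.2 allows a treated patient's data to be deleted on request with no exception for safety records, which conflicts with the reporting duties in 12.3 and the ITT definition in 7.2

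*Combined protocol and SAP*

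**What the plan says.** Section 17.2 describes a patient who interrupts the study as one who was enrolled and consented and who must "have been given the study intervention, but not completed the primary outcome for any reason". For such a patient, "If a subject interrupts the study the data collected will be used after acceptance from the patient". It then adds: "If the patient wishes that the collected data from acceptance to withdrawal from the study shall not be used, this data will be deleted". Sections 17.2 to 17.4 contain no carve-out for safety data, allocation or the fact of treatment.

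Section 12.3 sets safety duties without any condition on withdrawal:

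- "As we are testing a relatively new procedure, all AEs will be reported at every follow-up".
- "All AEs will be followed until satisfactory restitution or stabilizing of the patient".
- The timing, severity and consequences of each AE are also to be documented.
- Investigators are responsible for "reporting of all AEs and SAEs in the patient CRF and in the specific Trial Master File".
- A yearly safety report covers all SAEs and SARs.
- "Upon finishing the study an elaborate report containing all occurred SAEs must be made".

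Section 7.2 puts all eligible randomised participants in the ITT population and leaves the handling of missing values to a later plan. Section 10.1 makes REDCap the direct source for side effects found at follow-up and for rescue analgesic use after discharge. Section 17.4 has the reason for early withdrawal entered in the CRF.

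**The concern.** The deletion rule applies to patients who have already been treated, so it can reach the records that a safety evaluation depends on. For a patient who has an adverse event, withdraws before the primary outcome is complete and asks for deletion, 17.2 says the data go and 12.3 says the event is recorded and reported. The reason for leaving sits in the same CRF, so evidence that the departure was related to harm could be lost with the event.

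Three things are at stake: the completeness of the annual and final safety reports, the denominator for harms in each arm, and the ITT set. Section 12.3 itself describes the procedure as relatively new, and with 22 patients per arm a single record can carry all the information on an uncommon harm.

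**Working it through.** **1. The rules side by side**, for a treated patient with an incomplete primary outcome who asks for deletion:

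| Item | Under 17.2 | Under the other section |
|---|---|---|
| AE in the CRF | deleted | registered, followed and reported (12.3) |
| SAE | deleted, no exception stated | in the annual and final reports (12.3) |
| Outcome data | deleted | patient belongs to the ITT population (7.2) |
| Reason for leaving | in the CRF, so exposed | to be noted (17.4) |

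No section states an order of precedence.

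**2. Which records are exposed.** Several routes leave a copy outside the CRF. SAEs go to the sponsor within 24 hours, and AEs and SAEs also go in the Trial Master File (12.3). In-hospital adverse events come from the hospital record (section 14). Randomisation lists and envelopes are held separately (6.1, 6.2). For side effects found after discharge, 10.1 names REDCap as the source. Non-serious, post-discharge events are therefore the most exposed.

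**3. Timing.** The intervention is given 20-32 h after surgery (8.2), roughly postoperative day 1. The primary outcome ends on day 7 (3.1), about 6 days after treatment. Section 11.2 places severe dysesthesia 2-14 days after treatment. The overlap is about days 2-6 after treatment, or 5 of 13 days. However, 17.2 turns on an incomplete primary outcome and not on the date of leaving, so a patient with incomplete day 2-7 ratings who withdraws later could also be covered.

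**4. Expected number of cases.** Inputs: 2 of 169 patients with severe dysesthesia (11.2) and 22 per arm (4.2).

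- Expected cases: 22 × 2/169 = 0.26.
- Chance of at least one: 1 − (1 − 2/169)^22 = 0.23.

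No case is the likeliest result (77%). If one occurs, it may be the whole signal.

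**5. Worst-case effect of deletion.** The documents give no rate of deletion requests. Assume that k treated patients in one arm each have the event and have their data deleted, and that nobody else has it. Limits are exact (Clopper-Pearson). With no events among n patients, the upper limit is 1 − 0.025^(1/n).

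| k | True rate (95% CI) | Observed (upper limit) |
|---|---|---|
| 1 | 1/22 = 4.5% (0.1-22.8%) | 0/21 (16.1%) |
| 2 | 2/22 = 9.1% (1.1-29.2%) | 0/20 (16.8%) |
| 4 | 4/22 = 18.2% (5.2-40.3%) | 0/18 (18.5%) |

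If the separate randomisation list is used to restore the denominator, the observed result for any k is 0/22 (upper limit 15.4%). The event is still missing.

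**6. Effect on power.** The plan's sample size (7.1) reproduces. With SD 208 and a 50% reduction from 390, the difference is 195, and n = 2 × [208 × (1.960 + 0.842)/195]² = 17.86, rounded up to 18 per group. Losing 4 of 22 leaves 18, with 80% power by this formula and 78% by the t-test. Loss of nominal power is therefore not the main cost.

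**The case against.** The strongest reply is that deletion requires both a withdrawal and a specific request, and that serious events travel by routes that 17.2 does not clearly reach: notification of the sponsor within 24 hours, reports to the authorities, the Trial Master File and the hospital record. Nothing says that reports already made are recalled. A reader might infer from 17.2 that SAEs would vanish; the documents do not support that. This part stands, and it confines the main exposure to non-serious and post-discharge events.

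A reader might also infer that harmed patients are the likeliest to leave, so that the bias has a known direction. No section says who withdraws or who asks for deletion. That is a plausible risk and not a finding. Nor does the clause cover the whole 2-14 day window for dysesthesia, because a patient whose day 2-7 ratings are complete is not within its definition.

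A further reply is that 12.3 has AEs reported according to current law, section 15 invokes data-protection law, and the participant information and consent form, which were not available for review, may already say what is kept. These points do not remove the conflict. No section exempts safety records or says which rule prevails, and section 15 also commits the study to Good Clinical Practice. The consent documents should be checked, not presumed deficient.

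Finally, the intervals for 1/22 and 0/21 overlap heavily. That is so, and the comparison shows only what one record is worth in an arm of 22.

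**Conclusion.** The conflict is real and rests on the text alone: an explicit deletion rule without a safety exception, against unconditional duties to record and report adverse events and an ITT population of all eligible randomised patients. It needs no assumption about why patients leave.

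The size of the consequence does rest on assumptions. Under-counting of harms arises only if affected patients withdraw with an incomplete primary outcome and request deletion, and the documents give no probability for either step. The change from 1/22 to 0/21 is a worst case for one patient, not a forecast. The cost falls on safety ascertainment and the integrity of the ITT set far more than on power. This should be corrected before enrolment; it does not call the primary comparison into question.

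**What to change.** Amend 17.2 to say that after withdrawal no new data are collected without the patient's agreement, but that allocation, the fact and date of treatment, and AE and SAE records up to withdrawal are retained for the 12.3 reports and the safety denominator. Limit any deletion option to non-safety data. Section 12.3 should say how its duty to follow AEs applies after withdrawal, so that the two sections agree.

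Check that the participant information and consent form state the same rule. Report withdrawals and deletion requests by arm, and let the later statistical plan say how a patient whose efficacy data were deleted is counted in the ITT population and the CONSORT flow.

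The cost is a sentence or two in 17.2, a matching line in 12.3, and a sentence in the consent documents if they do not already have it. The downside is that patients lose the option of having safety records erased, and this must be disclosed before they consent.
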